Study Title “IVIg for Small Fiber Neuropathy With Autoantibodies to TS-
HDS and FGFR3”

NCT number: NCT03401073

Document Date: 11/29/2022

Protocol:

Study Design: This was a prospective 6-month double-blind placebo-controlled pilot study of IVIG for treatment of suspected immune mediated SFN associated with TS-HDS or FGFR-3. The trial was registered with ClinicalTrials.gov (NCT03401073).

Subjects: Potential research subjects were recruited from the panel of patients seen by neuromuscular/peripheral nerve groups at Beth Israel Deaconess Medical Center (BIDMC) (Boston, MA) and HonorHealth Neurology (Phoenix, AZ) and by patients seen at neighboring institutions in the Boston and Phoenix areas. Additional referrals were obtained through ClinicalTrials.gov. All recruited subjects provided signed informed consent as approved by the Institutional Review Boards of BIDMC and HonorHealth.

Inclusion Criteria: Patients were potentially eligible if they had clinically evident SFN in a length dependent or non-length dependent pattern as confirmed by history of symptoms that included burning, shooting, or prickling pain or dysesthesia for at least 6 months and examination findings demonstrating loss of pain sensation and/or loss of temperature detection in the distribution of pain. Subjects also required evidence of reduced intra-epidermal nerve fiber density (IENFD) seen on skin biopsy in the region corresponding to examination abnormalities, based on age and sex-matched normative values, using PGP 9.5 as the immunostain.¹⁵ Subjects required a baseline daily pain score on a visual analogue scale (VAS) of greater than or equal to 4/10. Patients also required elevated titers of autoantibodies to TS-HDS or FGFR-3 as measured by the Neuromuscular Clinical Laboratory at Washington University in St Louis using standard enzyme linked immunoassay (ELISA) assays as previously published.^{14,16} Antibody titers were measured at the time of screening and abnormal values measured at the Washington University laboratory within the 6 months prior to screening were accepted. Normative values are <10,000 for TS-HDS and <3,000 for FGFR3.

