Exclusion Criteria: Individuals were excluded if they had evidence of large fiber neuropathy such as abnormal nerve conduction studies, motor weakness, absent vibration, proprioception or deep tendon reflexes. Individuals were also excluded if they were found to have other known causes for small fiber neuropathy: diabetes, prediabetes, HIV, Sjogren's syndrome, vitamin deficiency, toxin exposure, or monoclonal gammopathy. Patients were also excluded for generalized, severe musculoskeletal conditions other than SFN that would have prevented accurate assessment by the physician, or for an underlying condition that would put them at risk of complication from a biopsy such as anticoagulant use.

or high risk of infection. Other exclusions were a contraindication to IVIG because of renal dysfunction with creatinine >1.5 mg/dl, prior thrombotic event or a hypersensitivity reaction to IVIG in the past.

Screening: Study subjects underwent a detailed history, physical examination, laboratory studies, pain VAS scores, the Short-Form 36 question health survey (SF-36), antibody measurement of TS-HDS and FGFR-3 and skin biopsy evaluation of nerve fiber density at the distal leg and proximal thigh using standard methodology.

Randomization and Blinding: Subjects who were eligible for study inclusion were block randomized into 2 groups (IVIG or placebo) by a blinded statistician. All study personnel, study subjects and support staff were blinded to treatment assignment. Only the single research pharmacist who mixed the IVIG/placebo was aware of the treatment assignment and was not in communication with any study staff. IVIG and placebo were placed in opaque infusion bags that covered the entire treatment product and infusion line to prevent unblinding.

Study Medication and Treatment Allocation: Subjects received either IVIG or placebo. IVIG treatment involved an initial dose of 1 gm/kg (Gamunex, Grifols, Los Angeles, CA) daily for 2 days followed by 1 gm/kg in a single dose every 3 weeks for 21 weeks (for a total of 8 doses) with a maximum of 80 gm IVIG infusion. Normal saline was used as placebo and included in a volume equivalent to that of IVIG.

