Study Procedures: The outline of the study protocol is seen in Supplemental Figure 1. At all study visits participants underwent review of inclusion and exclusion criteria, medical history, medication review, adverse effect review, and pain VAS scores (0-10 scale – reported as pain on the day of visit). At the screening and final study visits all subjects also completed skin biopsies at the distal leg,¹⁷ the Utah Early Neuropathy Scale (UENS),¹⁸ and the SF-36.¹⁹

Physical Examination: Detailed neurologic examinations were performed at baseline and at the final visit. The physical examination was quantified via the UENS.¹⁸ In brief, the UENS is a 42-point system that grades neuropathy from 0 (no neuropathy) to 42 (absent ankle reflexes, weakness at the toes, absent sensation to multiple modalities in the legs).

Pain Scores: Subjects rated their pain on an 11-point visual analogue Likert scale at every visit (where 0 = no pain and 10 = maximal pain). The location, exacerbating factors and character of pain were recorded at each visit. Subjects were treated with medications to reduce neuropathic pain at the discretion of the treating physician, including anti-convulsants, anti-depressants and opioids, typically in combination. Pain scores were measured while on medication. Subjects

were asked not to change doses of daily neuropathy pain medications while participating in the clinical trial. Subject use of pain medications was monitored at each study visit.

Skin Biopsy Evaluation of Intra-Epidermal Nerve Fiber Density (IENFD): All study participants underwent 3-mm punch skin biopsies 10 cm above the lateral malleolus at their baseline visit. Follow-up biopsies were taken 21-25 weeks later on the same leg adjacent to the original biopsy sites using standard techniques. Specimens were fixed and stained with PGP 9.5 (ubiquitin hydrolase, Chemicon).²⁰ All patients underwent IENFD counting by a blinded physician and results were expressed as a linear density for IENFD (number of fibers per millimeter).²¹

Statistical Analysis Plan:

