Primary Outcome: The primary efficacy endpoint for this study was the change in IENFD between visits 1 and 8. We defined a clinically relevant change in disease endpoint as a >2.0 fiber/millimeter increase in IENFD between screening and final visit. We anticipated no change in IENFD between visits 1 and 8 in the placebo treatment arm. The change in IENFD was based on prior studies of lifestyle modification in diabetic neuropathy where increases in IENFD of >2 fibers/mm over 1 year were seen in 25% of patients associated with an improvement in neuropathic pain.²² Pain was not selected as a primary outcome measure because a separate ongoing clinical trial using IVIG in small fiber neuropathy was already investigating pain as an endpoint,² and also because of our specific interest was in evaluating IVIG for potential impact on disease modification.

Secondary Outcomes: Two secondary outcome measures are included in this study:

- 1) The change in neuropathic pain severity between visits 1 and 8.

We expected that individuals with immune mediated small fiber neuropathy treated with IVIG would have a >2-point reduction in neuropathic pain VAS score between screening and final visit. We anticipated a <1.5-point reduction in neuropathic pain VAS score between screening and final visit in the placebo group.

- 2) The change in quantified UENS scores, between screening and final visit.

We expected that individuals with immune mediated SFN treated with IVIG would have a >1 point reduction in the UENS score between screening and final visit. We expected that the placebo treated group would have no change in UENS score between screening and final visits.

Exploratory Outcomes: Safety in response to IVIG infusion and changes in distribution or character of pain associated with SFN in patients treated with IVIG.

This pilot study was being conducted in order to obtain adequate preliminary data for a larger clinical trial but was powered to answer the primary endpoint analysis. Secondary endpoints and exploratory endpoints are not included in the power analysis. The sample size of 10 participants per group was determined with an assumed change in IENFD rate of 0 fibers/millimeter in the placebo group and >2.0 fibers/millimeter in the IVIG group, a 1-sided α of 5%, and 80% power between the 2 groups, including the assumption of a dropout rate of 10% (2 patients). Therefore, the aim was to include in total 20 patients in the study.

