The results were analyzed according to the intention-to-treat (ITT) protocol. For the primary ITT analysis, missing values were imputed as no change from baseline. Participants were analyzed for efficacy according to randomized treatment. For the SF-36 Health Survey, biopsy results, and UENS examination findings, the difference between baseline (screening period) and the end of the final visit was calculated. For the primary outcome measure, the proportion of patients with a decrease of at least 2.0 fibers/millimeter was compared between the IVIG and placebo groups with a χ^2 test, with mean and standard deviations reported. For secondary outcome measure, mean change in values between groups was compared using a student's T-test (2 tailed, 2 sample, homoscedastic variance). For pain VAS scores, ANOVA was used to measure differences in pain scores between IVIG and placebo groups.

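### Adjusting the UENS and pain comparisons for their collected baselines would be a cheap, low-priority improvement

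*Combined protocol and SAP*

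**What the plan says.** All references are to the Combined protocol and SAP.

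- **Outcomes.** Secondary Outcomes lists two. The first is pain: "The change in neuropathic pain severity between visits 1 and 8". The second is the UENS change from screening to the final visit.
- **Tests.** The last paragraph of the Statistical Analysis Plan takes UENS as a baseline-to-final difference. It then states: "For secondary outcome measure, mean change in values between groups was compared", by a two-tailed, equal-variance, two-sample t-test. A separate sentence reads: "For pain VAS scores, ANOVA was used to measure differences in pain scores between IVIG and placebo groups". Neither names a covariate, and baseline adjustment appears nowhere in the document.
- **Baselines available.** Physical Examination, where the examination is scored by UENS: "Detailed neurologic examinations were performed at baseline and at the final visit". Pain Scores: "Subjects rated their pain on an 11-point visual analogue Likert scale at every visit".
- **Allocation.** Randomization and Blinding: "Subjects who were eligible for study inclusion were block randomized into 2 groups (IVIG or placebo) by a blinded statistician". No stratification by baseline pain or UENS is described.
- **Entry limits.** Inclusion Criteria: "Subjects required a baseline daily pain score on a visual analogue scale (VAS) of greater than or equal to 4/10". Exclusion Criteria remove patients with "evidence of large fiber neuropathy such as abnormal nerve conduction studies, motor weakness, absent vibration, proprioception or deep tendon reflexes".

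**The concern.** With so few patients, the arms can easily start at different levels of pain or UENS. Blocking balances the numbers per arm, not the baseline scores. A change score does not fully correct for a different starting level unless the slope of final on baseline value is 1. A final score does not correct for it at all. The information needed to correct is already collected, so leaving it out gives up something for nothing.

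At stake are the secondary treatment differences in a pilot meant to inform a larger study: each estimate depends on the imbalance that happened to occur, and its interval may be wider than it need be. The Statistical Analysis Plan leaves these outcomes out of the sample-size calculation, and the primary IENFD result is not touched.

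A smaller point of clarity goes with this. The ANOVA sentence does not say which pain score it uses (final, change or repeated), and the t-test sentence may or may not cover pain change as well.

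**Working it through.** **Figures in the plan.** None is given for the UENS or pain analyses, so there is nothing to reproduce. The only input taken from the document is n = 10 per arm (18 analysed in total if the assumed two dropouts occur). The baseline-final correlation ρ and the SDs are not given and are varied below.

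**Step 1: how often the arms differ at baseline.** In baseline SD units, the difference in means has SD √(2/10) = 0.447. The chance that it exceeds 0.5 SD in either direction is P(|Z| > 0.5/0.447) = P(|Z| > 1.118) = 0.264.

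**Step 2: what that does to the estimate.** Let k = SD_baseline/SD_final and β = ρ/k. Given a baseline difference D, the unadjusted change-score difference has expectation (true effect) − (1 − β)D, and a final-score difference has (true effect) + βD. For example, with β = 0.5 and D = 0.5 SD, each is displaced by 0.25 baseline SD. The ANCOVA estimate is not displaced. Averaged over all randomisations D is zero, so no method is biased overall.

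**Step 3: precision.** Assume bivariate normal scores and a common slope. With 10 per arm, chance imbalance costs ANCOVA a factor 1 + 1/(2n − 4) = 17/16, so

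Var(ANCOVA)/Var(change) = (17/16)(1 − ρ²)/(1 + k² − 2ρk).

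| ρ | 0.3 | 0.5 | 0.7 | 0.8 | 0.9 |
|---|---|---|---|---|---|
| k = 1 | 0.69 | 0.80 | 0.90 | 0.96 | 1.01 |
| k = 0.9 | 0.76 | 0.88 | 0.99 | 1.03 | 1.06 |
| k = 0.75 | 0.87 | 0.98 | 1.06 | 1.05 | 0.95 |

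Worked cell, k = 0.75 and ρ = 0.5: 1.0625 × 0.75/0.8125 = 0.98. Simulation with 200,000 trials per cell agrees for k = 1 and k = 0.75. Mean 95% interval width ratios are 0.83, 0.90, 0.95, 0.98 and 1.01 at k = 1, and 0.94, 0.99, 1.03, 1.03 and 0.98 at k = 0.75.

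The rows with k < 1 matter because the pain threshold of 4/10 plausibly narrows baseline pain. Excluding weakness and absent reflexes, which UENS scores, may do the same for UENS.

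**Step 4: the worst case.** The ratio is largest at ρ = k (β = 1), where it equals 17/16, a 6.25% loss. With 9 per arm the factor is 1 + 1/14 = 15/14, a 7.1% loss, and the interval is about 4% wider once the lost degree of freedom is counted. Eighteen analysed is a realistic case, because the rule imputing no change is stated only for the primary analysis.

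**Step 5: if the pain ANOVA uses final scores only.** With equal SDs the ratio is (17/16)(1 − ρ²): 0.97, 0.80, 0.54 and 0.38 at ρ = 0.3, 0.5, 0.7 and 0.8.

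**Step 6: type I error (simulated, no effect, k = 1, ρ as in the table).** For the change-score test it is 11%, 10%, 8%, 7% and 6% in the 26% of trials with imbalance above 0.5 SD, 2.7% to 4.7% in the rest, and 5% overall. ANCOVA is at 5% in both subsets.

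**Step 7: absolute power (two-sided 5%, SDs assumed).** For a pain contrast of 2 − 1.5 = 0.5 points, SD 2 and ρ = 0.5, power goes from 8% to 9%. For a UENS contrast of 1 point, SD 3 and ρ = 0.5, it goes from 11% to 12%. The expected effects in Secondary Outcomes are bounds, so these contrasts are illustrations only.

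**The case against.** The strongest reply is that this is a choice between two valid estimators. The outcomes are defined as changes, a t-test on mean change estimates exactly that, it holds its type I error, and its standard error already contains chance imbalance. The documents give no ρ or SD, and under some plausible values ANCOVA is slightly less precise: at k = 0.75, for ρ between about 0.54 and 0.87.

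Most of this stands, and it is why the point has low priority. It does not remove the point, because adjustment also frees the estimate from the imbalance that actually occurs, and its price is small and bounded.

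Four stronger readings are tempting, and the documents do not support them:

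- **That the planned tests are biased or inflate type I error.** Over randomisation they are and do neither. The raised rates in Step 6 apply only to the imbalanced subset and are offset in the rest. The pain threshold may cause regression to the mean, but it acts on both arms alike.
- **That the pain outcome is undefined.** Secondary Outcomes fixes it as the change from visit 1 to visit 8. Pain is the first secondary outcome, so the t-test sentence can be read as covering it, with the ANOVA as an additional analysis. What is unclear is the ANOVA, and that is a matter of wording.
- **That the secondary estimates and intervals are what the next trial will be built on.** The plan says only that the pilot is to yield preliminary data. It does not say which estimates will be used.
- **That the loss can never exceed 6.25%.** This holds only with 20 patients analysed.

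**Conclusion.** The point holds as a cheap, low-priority improvement, not as an error. UENS change certainly, and pain change possibly, is compared by an unadjusted t-test, and pain scores by an ANOVA with no named covariate, although both baselines are on hand. About one trial in four of this size would have a baseline gap above 0.5 SD, and the unadjusted change estimate would then be off by (1 − β) times that gap.

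The effect on precision ranges from a variance reduction of about 31% (equal SDs, ρ = 0.3) to a loss of at most 6.25% (20 analysed) or 7.1% (18 analysed), the loss being reached near β = 1. These figures rest on assumed correlations and SD ratios, approximate normality and a common slope. Adjustment does not rescue power, which stays low in both illustrations.

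**What to change.** - Analyse UENS (screening to final visit) and pain VAS (visit 1 to visit 8) by ANCOVA: final value or change on treatment, with the baseline of the same measure as covariate. Either form gives the same treatment estimate.
- State that this is the single analysis of the pain change defined under Secondary Outcomes, so that the t-test and ANOVA sentences no longer compete.
- Report each adjusted difference with a 95% confidence interval.
- If the adjusted analysis is specified after unblinding, label it post hoc. The document is dated 11/29/2022 and describes the analysis in the past tense, so this label may well be needed.

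The cost is a few lines of SAP text and one degree of freedom per outcome, plus the bounded variance loss given above. No new data are needed and the primary analysis stays as it is.
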